The secondary aim of this study is to assess the effects of 12-weeks of endurance exercise training on WAT-specific IR and fasting FFA levels and molecular adaptations in skeletal muscle that may contribute to the alterations in WAT.

Approach: Blood samples and dialysates from abdominal subcutaneous WAT will be collected during hyperinsulinemic clamp to assess whole-body IR and WAT-specific suppression of lipolytic rates under physiological insulin in men and pre-menopausal women with obesity. A skeletal muscle biopsy from the vastus lateralis will be collected before and after 12 weeks of deuterium (2H) labelled water administration and endurance exercise training to assess transcriptomic and proteomic adaptation that may associate with WAT adaptations.

Study Design

Research Design

This is a double-site (AH TRI and PBRC), longitudinal (12 weeks) randomized clinical trial with two groups; a control group (CTRL) and an exercise training group (EX)

Research Intervention Description

Subjects will be submitted to 12 weeks of supervised aerobic exercise training intervention and oral deuterium-labelled water administration OR oral deuterium-labelled water administration only.

This study consists of a Screening Period, Baseline Period, Intervention Period, and Follow-up Period, detailed below.

Study Site(s)/Location(s) and Number of Subjects

AdventHealth Orlando Sites: Translational Research Institute (TRI)

Estimated number of subjects at AdventHealth Orlando site: 35 men and women (accounting for a 20% dropout; we expect 29 to complete the study)

Name of external site(s) outside of AdventHealth Orlando: Pennington Biomedical Research Center

Estimated number of subjects at external sites: 35 men and women (accounting for a 20% dropout; we expect 29 to complete the study)

Total number of all sites: 2

Estimated number of subjects at all sites combined: 70

Multi-Site Research Logistics/Communication Plan

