The primary aim is powered to detect differences in the change in *in vivo* formation of new adipocytes (i.e., fraction of newly formed adipocytes; "f") of subcutaneous WAT between the CTRL and EX groups. We hypothesize that the EX-group will have a decrease in the fraction of newly formed adipocytes in response to the EX intervention as compared to the CTRL group. Analysis of women from our previous VIVA study (NCT03530111) indicates that the mean value of "f" in the physically active (exercise) group is 11.4%, while the sedentary group has an "f" value of 17.8%. Because VIVA only has crosssectional data (assessment at one time-point), we must also use data from the Apple & Pear study (NCT01748994) 9 to estimate the change in fraction of newly formed adipocytes, as the proposed study includes an exercise intervention. By utilizing data from the CTRLgroup in the Apple & Pear study 9 (baseline assessment) and increasing the estimate to ensure that the study is well-powered, we can estimate the CTRL and EX groups from the proposed study to have an overall mean "f" value of 17% (at baseline) with a standard deviation of 6.0%. A total sample size of 58 (assuming a ~17% overall lost-to-follow-up rate) will provide at least 80% power to detect significant differences in "f" between the CTRL and EX groups, with a 5% significance level.

Current Version Date: 08/05/2024 IRBNet #: 1805407
Page 29 of 42

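### Does the 20% dropout quoted for each site undermine the target of 70 enrolled and 58 completers?

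*Protocol*

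**What the plan says.** The figures stand in two places in the protocol.

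- **Study Site(s)/Location(s) and Number of Subjects.** For the coordinating site: "Estimated number of subjects at AdventHealth Orlando site: 35 men and women (accounting for a 20% dropout; we expect 29 to complete the study". For the other site: "Estimated number of subjects at external sites: 35 men and women (accounting for a 20% dropout; we expect 29 to complete the study". The total is then given: "Estimated number of subjects at all sites combined: 70".
- **Sample Size Determination.** "A total sample size of 58 (assuming a ~17% overall lost-to-follow-up rate) will provide at least 80% power".

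So the site listing attaches 20% to a fall from 35 to 29 at each site, while the power section attaches about 17% to the total of 58.

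**The concern.** The mismatch shows within a single line: 20% of 35 is exactly 7, which leaves 28, so rounding cannot produce 29. The same line appears for both sites, so it is not a stray digit in one place. The protocol also gives two different loss rates for what appears to be the same step from enrolled to analysable participants.

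If 20% were the rate the sponsor really expects, 70 enrolled would yield 56 completers, two fewer than the number on which the power statement rests. Keeping 58 would then need a larger enrolment. An inflation for dropout that falls short of the required completers is a familiar planning error and deserves a check.

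**Working it through.** **Inputs.** From the site listing: 35 enrolled per site, 20% dropout, 29 completers per site, 70 enrolled in total. From Sample Size Determination: 58 in total, about 17% loss, at least 80% power, 5% significance level. From Randomization: 1:1 allocation.

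**1. Do the counts agree with each other?** 35 + 35 = 70 and 29 + 29 = 58. The second sum also shows that the 58 in the power section is the number completing, not the number enrolled.

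**2. Which rate do the counts imply?** Loss = 1 − completers / enrolled.

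- Per site: 1 − 29/35 = 6/35 = 17.1%
- Overall: 1 − 58/70 = 12/70 = 17.1%

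**3. Does the rate in the power section reproduce the enrolment?** Enrolled = completers / (1 − loss).

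- At 17%, per site: 29/0.83 = 34.9, so 35
- At 17%, overall: 58/0.83 = 69.9, so 70

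Both stated enrolments are recovered.

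**4. Does 20% reproduce them?**

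| Calculation at 20% | Result | Stated |
|---|---|---|
| 35 × 0.80 | 28 | 29 |
| 70 × 0.80 | 56 | 58 |
| 29/0.80 | 36.25, so 37 | 35 |
| 58/0.80 | 72.5, so 73 | 70 |

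None of the four matches.

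**5. Where might the 20% come from?** Adding 20% to the completers gives 29 × 1.2 = 34.8, so 35, and 58 × 1.2 = 69.6, so 70. Expressed as a share of those enrolled, such a mark-up is 0.20/1.20 = 16.7%, again about 17%. The protocol does not state this origin, so it is an inference.

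**6. What if 20% really were lost?** The protocol gives neither the sidedness of the test nor the target difference in change, so its 80% cannot be rebuilt from first principles. Assume instead a two-sided 5% two-sample t test, equal arms, and power of exactly 80.0% at 29 per arm. The same standardised effect at 28 per arm gives 78.56%, a loss of 1.44 percentage points. With the stated SD of 6.0 on the analysed scale and a normal approximation, the difference detectable at 80% power is (1.960 + 0.842) × 6 × √(2/n): 4.41 points at n = 29 and 4.49 points at n = 28.

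**The case for a change.** The strongest case for acting is that the sentence is wrong as written and cheap to put right. A dropout rate is a share of those enrolled; a mark-up on completers is something else, and the protocol does not say that a mark-up was meant. Two rates for the same quantity invite confusion: 20% of 70 permits 14 losses, whereas 58 completers permits only 12. Since the sites are to discuss enrolment regularly and the monitoring committee is to review accrual, they would be better served by one rate.

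The arithmetic in that argument stands, and replacing 20% by about 17% in the two site lines would be a harmless tidy-up. The practical consequence does not stand. No retention threshold, replacement rule or stopping rule in the protocol refers to 20%. Withdrawal is decided participant by participant (Early Withdrawal of Subjects), and the committee's listed topics under Safety Monitoring set no limit on dropout. Anyone following retention also finds the expected 29 completers in the same line as the 20%. The case for a power shortfall requires the sponsor to expect a true 20% loss, against the four counts and against the rate in the section that governs sample size.

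**Conclusion.** The inconsistency is real but clerical. Four counts (35, 29, 70, 58) and one rate (about 17%) agree; only the 20%, printed once for each site, does not. The gap is one participant per site and two overall, in lines that are worded as estimates.

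No change to the plan follows, because correcting the percentage would leave everything that matters where it is: 70 enrolled, 58 completing, the stated power and the analysis. A sponsor following the protocol as written would recruit the same number and reach the same results.

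This rests on reading the 58 as completers, which the site totals support, and on the roughly 17% in Sample Size Determination being the rate the sponsor intended, which the enrolment of 70 supports. Should 20% prove to be the true loss, the cost would be about 1.4 percentage points of power under the assumptions in step 6, and less if power at 58 is above 80%.

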AdventHealth IRB will be the IRB of record for both sites, and AdventHealth will be the coordinating center. The two participating sites will meet via teleconference or phone call on a regular basis to discuss any issues, recruitment strategies, enrollment status, safety concerns, and any changes to the study protocol or supporting documents. [name] and [name] have known each other for over a decade and have complementary skill sets in adipose tissue metabolism, as well as working closely together on the Program Planning Committee for The Obesity Society (TOS) for the past several years. Both investigators have done in-person site visits in the last 2 years in order to align their common laboratory practices related to this project, in addition to meeting virtually on a bi-weekly basis to plan this project. This project represents a continuation of the strong collaborations between AH TRI and PBRC. AH TRI and PBRC are both clinical sites in MoTrPAC (U01AR071133) and thus aligned and cross-validated for all clinical assessments, procedures, WAT processing and the exercise intervention. In broader terms, AH TRI and PBRC have long outstanding track records in leading multi-site lifestyle modification interventions in studies funded by the NIDDK (MoTrPAC, DPP, LookAHEAD), NIA (CALERIE 1 and 2, LIFE), and USDA (PROOF). While the proposed study will capitalize on our sites' participations in MoTrPAC and align our overlapping clinical procedures and intervention accordingly, we cannot execute this as an ancillary to MoTrPAC due to the prospective nature of the ²H₂O labeling, hyper-insulinemic clamp and large tissue requirements for the downstream assays. We have chosen to conduct this clinical exercise trial at two sites to maximize efficiency through use of common core capabilities and complementary benchbased methods, to ensure successful completion of the enrollment goals, as well as enhance our ability to include African Americans (mainly from the PBRC population) and Hispanics (mainly from the AH TRI population).

Research Conducted in a Foreign Country

N/A

Community-Based Participatory Research

N/A

Subject Selection

Vulnerable Populations (if applicable)

Cognitively Impaired Adults: N/A

Children: N/A

Pregnant Women: N/A

Neonates of non-viable or uncertain viability: N/A

Prisoners: N/A

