Waiver or Alteration of the Consent Process (consent will not be obtained, required information will not be disclosed, or the research involves deception)

N/A

Waiver or Alteration of HIPAA Authorization

Partial waiver of HIPAA authorization will be requested.

Non-English Speaking Subjects

We intend to enroll only English-speaking participants due to the complexity of the study procedures and the lack of translational capacity that could be adequately provided throughout the duration of the study.

Randomization

Men and women will be randomized to the CTRL and EX groups on a 1:1 basis following successful completion of the VO₂max test and imaging tests. Participants will be stratified by sex to ensure balance between each of the groups. Stratifying allows for different sample sizes in each sex, but ensures that within each sex, there are an equal number of treatments and controls.

Study Visits

Study visits will be conducted at the AdventHealth Translational Research Institute or Pennington Biomedical Research Center.

Screening Visit (SV) (Outpatient; Approximate visit time: 2 hours)

Participants will arrive for this outpatient visit after a 10 hour overnight fast. After obtaining informed consent, data collection for assessing eligibility will commence. The screening visit will include:

¹Urine for pregnancy test (if applicable), urinalysis, and toxicology screen (Amphetamine, Barbiturate, Benzodiazepine, Cocaine, Methadone, Opiate, THC, Cannabis, Tricyclics, and Oxycodone)

²Demographics and complete medical history (including, but not limited to, alcohol use, concomitant medications, health conditions, allergies and exercise habits)

³Vital signs (respiratory rate, temperature, heart rate, blood pressure)

⁴Standard physical examination performed by a study physician, physician assistant, or nurse practitioner

⁵Anthropometrics including height, weight, waist circumference, and BMI

⁶Screening blood draw to measure CBC with differential and platelets, comprehensive metabolic panel (CMP), lipid profile, blood glucose, HbA1C, ALT, AST, alkaline phosphatase, insulin level, and TSH

⁷Electrocardiogram (ECG)

⁸Consent Process Checklist assessing the potential participants' understanding of and willingness to perform all study activities.

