⁶**Randomization**: Once a participant passes screening, completes the VO₂max test, and is considered eligible to continue in the study, they will be randomized in a 1:1 ratio into either the control (CTRL) group or the exercise group (EX). Randomization will be conducted by a statistician.

Baseline Period – Visit 2 (V2)

Day-8 (± 2): In patient. Participants will report to the local site the evening of day -8 for an overnight stay. A single urine collection will be done for measurements of urea, nitrogen, and creatinine. Participants will then receive a standardized dinner meal (10 kcal/kg; 50% carbohydrate, 15% protein, 35% fat), and be strongly encouraged to consume all food provided. Any unconsumed food will be recorded. Participants will remain fasting from completion of evening dinner meal at the local site until WAT biopsy and hyperinsulinemic-euglycemic clamp protocol are completed the following day.

¹Surveys (Optional):

With the exception of the Diet History Questionnaire (DHQ) III, all surveys will be administered to participants via the password protected computer-based software REDCap.

- **Diet History Questionnaire (DHQ) III:** Approximate duration: 10 min; the DHQ-III, owned by the NIH National Cancer Institute will be completed through the NIH-developed secured platform specific for this instrument. Participants will complete the DHQ-III under their assigned PID during the clinic visit and no personal identifiers will be obtained.
- Retrospective Visual Analog Scale (VAS): Approximate duration: 5 min; an 8-item retrospective VAS assessing appetite, including hunger, fullness after meals, thoughts of food, cravings, and urges to eat.
- Three Factor Eating Questionnaire (TFEQ): Approximate duration: 5 min; an 18item questionnaire assessing cognitive and behavioral components of eating and comprises 3 different scales corresponding to cognitive restraint, emotional eating, and uncontrolled eating.
- **Food-Craving Inventory (FCI):** Approximate duration: 5 min; a 33-item self-report measure of general and specific food cravings relating to overeating and binge eating.
- MacArthur Socioeconomic Status Index: Approximate duration: 6 min; an 11-item questionnaire regarding participants' perception of their socioeconomic status relative to their community and country, their living situation, level and degree of education obtained, job status, income, and debt.

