⁸Respiratory Quotient (RQ): Indirect calorimetry will measure the respiratory quotient (RQ) and substrate utilization using either a ParvoMedics Metabolic Cart at TRI (Salt Lake City, UT) or Omnical Cart at PBRC (Maastricht Instruments BV). The ParvoMedics Metabolic Carts are calibrated daily before each subject with standardized gases containing

1% CO₂, 16% O₂ and balance N₂. The Omnical Carts are also calibrated daily before each subject with standardized gases containing 0.8% CO₂, 18% O₂ and balance N₂ and then self-calibrate continuously through the test approximately every 15 minutes. After inserting the clamp catheters, completing the WAT and muscle biopsies, and inserting the microdialysis catheters, and allowing flushing of the microdialysis catheters for 5 minutes, participants will rest for 60 minutes laying down in a Semi-Fowler's position. After 30 minutes of dialysate collection, a transparent plastic hood connected to the device will be placed over the head of the subject. Calculations of O₂ consumption (VO₂) and CO₂ production (VCO₂) will be made by comparing measures of the O₂ and CO₂ concentrations of the testing room (measured every 5 minutes at TRI and every 2 minutes at PBRC) to continuous measurements of O₂ and CO₂ concentrations in expired air diluted in a constant air flow (15-30 L/min at TRI and 85-90 L/min at PBRC) generated by a pump. From the above, energy expenditure standardized for temperature, pressure, and moisture will be calculated at one-minute intervals. After ~30 minutes, the remaining clamp procedures will resume. This will be repeated during steady state 1 (+90-120min) and steady state 2 (+210-240mins).

Standardized Meal and Accelerometer: After all procedures are complete, participants will be provided a standardized meal along with post procedure instructions. Participants will also be provided with a triaxial activity monitor (Actigraph GT3X) which will be worn for 7-10 days. The monitor integrates motion sensor data from the tri-axial accelerometer to estimate the energy cost of free-living activity. The participant will wear the monitor at

all times, except while showering or bathing. After the period of wear time, the participant will return the monitor and the data will be uploaded.

¹⁰7-Day Food Record (optional): Participants will be asked to record their food and beverage intake for 7 days and return the form to the research site at their next in-person visit.

Phone Follow-up After Baseline Visit 2

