Single nuclei RNAseq Power Calculation. To date the most comprehensive analysis of human WAT has been conducted by Emont and colleagues who performed snRNAseq in whole frozen WAT and VAT from humans with obesity and established 17 subpopulations of cells. However, these data were generated using the 10X Genomics platform. We have published preliminary snRNAseq data in WAT from 22 individuals with overweight and obesity. We expect to capture nuclei from the WAT that may reveal up to 12 different cell populations (Fig. 4). If we assume the rarest cell type is 2% and require at least a 100 of the of rarest cell type to accurately quantify and describe it, we require a total of 6,792 nuclei to achieve a 99% probability of meeting these requirements. Our current technique permits 1400 cells per participant to be analyzed which equates to 28,000 cells for 20 participants at each timepoint in EX-group and 14,000 nuclei for 10 participants at each timepoint in the CTRL-group. This would allow us to accurately define subpopulations within WAT and generate sufficient data to compare the impact of endurance exercise on adipocyte populations and non-adipocyte populations.

Statistical Analysis Plan

Primary and Secondary Objective Analysis

Shapiro-Wilk test will be initially performed to assess the normality of data and homogeneity of variances. Pre- and post-intervention results will then be tested by paired t-test or Wilcoxon signed-rank test, as appropriate. Results will be expressed as mean \pm standard deviation and significance will be established, *a priori*, at p≤0.05.

Potential Risks and Benefits

Potential Benefits

The potential benefits to an individual participant in this study are not known. Exercise training can trigger many beneficial adaptations, but individual responses and adaptations vary. All participants will acquire knowledge about their physiological status (e.g., cardiorespiratory fitness, body composition, etc.) that may be of personal benefit. The risks presented to participants are minimal, and information gained from this project will be useful to identify mechanisms responsible for exercise effects on adipose tissue quality and insulin resistance in subjects with obesity.

Potential Risks

Described below are all the known risks of being in this study.

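### The tests fixed in the protocol have no term for sex, the stratification factor, or for site; an EX versus CTRL model with both would recover some precision at almost no cost

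*Protocol*

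**What the plan says.** - **Randomization:** allocation is 1:1 and "Participants will be stratified by sex to ensure balance between each of the groups". The stated purpose is equal numbers per arm within each sex. No other factor is named.
- **Baseline Period – Visit 1, Randomization:** "they will be randomized in a 1:1 ratio into either the control (CTRL) group or the exercise group (EX". Again no further factor is named.
- **Research Design; Study Site(s)/Location(s) and Number of Subjects:** "This is a double-site (AH TRI and PBRC), longitudinal (12 weeks) randomized clinical trial with two groups". Each site is to enrol 35, for 70 in all, with 29 per site expected to complete.
- **Multi-Site Research Logistics/Communication Plan:** one reason for using two sites is to "enhance our ability to include African Americans (mainly from the PBRC population) and Hispanics (mainly from the AH TRI population". The same section describes the sites as aligned and cross-validated for assessments, tissue processing and training.
- **Endurance Exercise Training:** one programme, delivered at whichever site the participant attends.
- **Statistical Analysis Plan, Primary and Secondary Objective Analysis:** "Pre- and post-intervention results will then be tested by paired t-test or Wilcoxon signed-rank test, as appropriate". There is no term for sex, site or arm.
- **Sample Size Determination:** the powered quantity is the difference between CTRL and EX in the change in the fraction of newly formed adipocytes (f).

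**The concern.** A factor important enough to stratify on should normally appear in the analysis. Stratification makes the arms more alike on sex than chance would. A between-arm test that ignores sex does not credit that balance, so its standard error is too large and the test is conservative.

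Site is a natural second factor. It is known before randomisation, and the protocol itself says the sites draw on different populations. Tissue is also obtained at each site, and cell isolation is listed under fresh procedures before freezing. Because site is not a stratum, the arms can be unequal within a site by chance. Because site is not in the analysis, nothing corrects for that afterwards. What is at stake is precision in a trial planned on 58 completers.

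**Working it through.** **The protocol's own figure.** Sample Size Determination gives 58 completers, a baseline SD of 6.0 points, a 5% level and at least 80% power. It states neither an effect size nor the SD of change, so 58 cannot be reproduced exactly. Taking 6.0 as the SD of change and a two-sided test (both assumptions), the detectable difference with 29 per arm is (1.960 + 0.842) × 6.0 × √(2/29) = 4.41 points, or 4.49 using the t distribution. Enrolment follows as 58/(1 − 0.17) = 69.9, so 70.

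**Chance imbalance by site.** Take 70 randomised, 35 per arm and 35 per site, with site not a stratum and the sex strata treated as one pool (an approximation). The number X at one site allocated to EX is hypergeometric: P(X = x) = C(35,x)·C(35,35−x)/C(70,35).

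- 20/15 or worse: 33.9%
- 21/14 or worse: 15.1%
- 22/13 or worse: 5.5%
- Among 58 completers (29 per site, 29 per arm), 18/11 or worse: 11.4%

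**What an imbalance does.** If the outcome differs by 3 points between sites (assumption), a 20/15 split moves the arm contrast by 3 × (20 − 15)/35 = 0.43 points. A 21/14 split moves it by 3 × (21 − 14)/35 = 0.60 points. Both are small against 4.4-4.5.

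**Value of adjustment.** If sex and site explain a share R² of outcome variance, the equivalent gain in participants is 1/(1 − R²) − 1.

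- R² = 0.05: 5% (58 act like 58/0.95 = 61)
- R² = 0.10: 11% (58/0.90 = 64)
- R² = 0.20: 25% (58/0.80 = 72.5)
- R² = 0: no gain

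The protocol gives no value for R². At SD 6.0 with even splits, a difference d contributes d²/4 to the variance. R² = 0.10 therefore needs d = √(4 × 0.10 × 36) = 3.8 points from one factor alone, or √(4 × 0.05 × 36) = 2.7 points from each of the two.

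**Simulation.** 4,000 trials per row, 58 completers, total SD 6.0, true difference 4.5, even sex split. The unadjusted test is a two-sample t-test; the adjusted test is a linear model with sex and site.

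| Assumed site / sex difference | R² | Power, unadjusted, sex strata | Power, adjusted, sex strata | Power, adjusted, site-by-sex strata | Type I error, unadjusted, sex strata |
|---|---|---|---|---|---|
| 0 / 0 | 0 | 0.801 | 0.794 | 0.808 | 0.051 |
| 3 / 0 | 0.06 | 0.802 | 0.816 | 0.822 | 0.050 |
| 3 / 3 | 0.125 | 0.793 | 0.834 | 0.846 | 0.042 |
| 0 / 4 | 0.11 | 0.825 | 0.846 | 0.846 | 0.035 |
| 4 / 4 | 0.22 | 0.812 | 0.881 | 0.884 | 0.040 |

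Monte Carlo standard errors are about √(0.8 × 0.2/4000) = 0.006 for power and √(0.05 × 0.95/4000) = 0.003 for type I error. With sex-only strata, the adjusted type I error stays between 0.044 and 0.052. The unadjusted test becomes conservative only where sex, the stratified factor, has an effect. Moving from sex-only to site-by-sex strata adds at most about 0.01-0.02 to adjusted power, which is close to simulation noise.

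**The case against.** Much of the case on the other side stands.

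- **Validity.** Sex-only stratification in a 70-person trial is sound. A reader might infer that arm is confounded with site. It is not: any imbalance is due to chance under randomisation, and the shifts above are small.
- **Equipment.** The calorimetry carts do differ by site ("using either a ParvoMedics Metabolic Cart at TRI", another model at PBRC). They measure respiratory quotient, which is not a listed outcome. A reader might also infer that the MRI scanner differs by site, but Visit 1 lists three scanners and assigns none to a site.
- **Training.** A reader might infer that each site runs its own exercise programme. The protocol sets one programme, with the same frequency, duration, heart-rate schedule and monitor at both sites; only the venue differs.
- **Assays.** The section on materials of human origin suggests that adipocyte formation and TG turnover are each measured in one place for both sites. That leaves local biopsy and cell handling as routes for a site effect, not the assay.
- **Within-person change.** A stable site offset largely cancels in change scores. This is less certain for adipocyte formation, because the baseline biopsy (Day -7) precedes the first labelled water.
- **Relevance to the stated test.** The standard-error argument applies to a between-arm comparison, and the stated paired test is not one. That the section contains no EX versus CTRL test is a separate and larger defect. Covariates matter only once it is repaired.

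One objection fails in part. Covariates, block sizes and list details can be left to documents not shown. Here, however, the protocol goes further and fixes named tests for the primary and secondary objectives that leave out its own stratification factor.

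**Conclusion.** The point holds as a modest, nearly free improvement. The protocol stratifies by sex and runs at two sites with different populations, and the tests it fixes use neither factor. The consequence is lost precision and uncorrected chance imbalance (15% for 21/14 or worse at a site), not bias.

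The size depends on an effect the protocol does not give. Adjustment is worth about 5-25% more participants if sex and site together explain 5-20% of variance, and essentially nothing if they explain none. In the simulated scenarios with sex-only strata, power moves from about 0.80 to between 0.79 and 0.88.

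Covariate adjustment carries nearly all of the benefit. The documents do not support a claim that the existing allocation is invalid or must be redone.

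**What to change.** 1. In the Statistical Analysis Plan section, specify for each outcome a between-arm (EX versus CTRL) model with sex and site as covariates, for example on the change or on the post value adjusted for baseline. The cost is two degrees of freedom (56 to 54 residual in the 58-completer model without a baseline term). No extra participants or procedures are needed.
2. Optionally, for participants not yet randomised, use separate site-by-sex lists (four strata) with small permuted blocks. The cost is a new list and a few incomplete blocks in small strata, since the sex split is not fixed. If enrolment is well advanced, step 1 alone recovers most of the gain.
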